Objective	
1. To evaluate the safety of an investigational version of the enlighten™ 532nm /1064nm/670nm laser for photo-rejuvenation.2. To evaluate the efficacy of an investigational version of the enlighten™ 532nm /1064nm/670nm laser for photo-rejuvenation.
Study Design	A single-center prospective, open-label uncontrolled exploratory study. Subjects will receive [REDACTED] laser treatments, [REDACTED] [REDACTED] and will be followed at 2 [REDACTED] [REDACTED] 12 weeks [REDACTED] post-final treatment. In addition, after each treatment, subjects will complete a 3 day post treatment phone follow-up. [REDACTED] [REDACTED]
Enrollment	A maximum of 20 subjects
Study Endpoints	
• Incidence and severity of adverse device effects at 2 weeks post-first treatment.• Incidence and severity of adverse device effects during the study period, including subject pain level during laser treatment.• Degree of improvement in the treated area at 12 weeks post-final treatment as assessed by the Investigator (Physician's Global Assessment of Improvement). [REDACTED]
Subject Population	Female or male subjects, age 18 to 75 years, Fitzpatrick skin types I-VI
Planned Schedule	First subject enrolled: September 2016 Last subject last visit: August 2018

1 PURPOSE

The purpose of this exploratory investigation is to evaluate the safety and efficacy of an investigational version of the Cutera enlighten™ laser for skin rejuvenation, specifically improvement of acne scars, fine rhytides, lentigines, pigmentation, erythema and skin texture. The version of the laser under investigation allows the user to treat using a wavelength between 660 nm – 690 nm as well as 532 nm or 1064 nm.

2 BACKGROUND INFORMATION

2.1 Photo-Rejuvenation

Non-invasive treatment options are in high demand by patients wanting to improve their appearance without surgical intervention. As a result, patients now have a variety of options for non-invasive skin rejuvenation, from laser and light-based treatments to devices that utilize ultrasound and radiofrequency, however this was not always the case. Initial skin rejuvenation procedures utilized ablative lasers, such as the carbon dioxide (CO₂) and erbium:yttrium-aluminum-garnet (Er:YAG), and resulted in substantial improvement in skin appearance, texture, rhytides and laxity[1-3]. Since ablative treatments destroy the epidermal layer of the skin in order to penetrate and heat the deeper dermal layers, ample post-procedure recovery time is required and patients may experience side effects lasting for a few weeks. Furthermore, hypo- or hyperpigmentation, prolonged wound healing and even scarring can occur following ablative procedures [4-6]. Treatment methods with less risk of side effects and post-treatment down time are in high demand. As such, the choices are vast and varied, ranging from non-ablative laser devices to those that use radiofrequency [7-15].

Laser therapy often includes the use of pulsed lasers, namely Q-Switched or Quality-Switched (QS) lasers which produce nanosecond laser pulses by suddenly releasing all of the excited-state energy from the laser medium [16]. This concept is based on the principle of selective photothermolysis which imply: (1) the use of the wavelength matching the absorption spectra of the pigment; and (2) the delivery of the heat to target pigment particle within pulse duration shorter than its thermal relaxation time [17]. This allows selective destruction of target chromophore in the skin with minimal damage to the surrounding tissue.

Nanosecond QS lasers have been widely used for more than 20 years as a safe and effective treatment for skin rejuvenation [18-24]. Laser wavelengths and pulse durations currently available for nanosecond QS laser treatment of pigmented lesions include 532 nm Nd:YAG, 1064 nm Nd:YAG, 755 nm Alexandrite and 694 nm Ruby with pulse durations from 5 to 10 ns (Nd:YAG), 50 to 70 ns (Alexandrite) 25 to 30 ns (Ruby). These wavelengths in the visible and infrared ranges are appropriate for the absorption spectrum of melanin. Melanin, the target pigment for these lasers, is largely present in basal keratinocytes in benign pigmented lesions. During laser procedures, the melanosomes, the organelle which hold the melanin in melanocytes, are rapidly heated [25, 26]. This rapid heating and evaporation of the melanosomes in the skin result in vacuolization.

The current proposed exploratory clinical study described herein intends to evaluate the safety and effectiveness of the investigational laser and the optimal range of treatment parameters for use in skin rejuvenation.

2.2 Study Device

2.3

[REDACTED]

[REDACTED]

[REDACTED]

[REDACTED]

[REDACTED]

3 STUDY OBJECTIVES

The objective of this study is to evaluate efficacy and safety of treatment with the investigational version of the Cutera enlighten™ laser with 670nm wavelength for photo-rejuvenation.

4 STUDY DESIGN

This is a single-center prospective, open-label, uncontrolled feasibility study in up to 20 male or female subjects, age 18 to 75 years who desire laser treatment for photo-rejuvenation, specifically improvement of acne lesions and scars, fine rhytides, lentigines or pigmentation, diffused redness erythema and skin texture. Subjects may be treated on the face and/or body (such as, but not limited to, hand, forearm, chest or décolleté).

Subjects will receive [REDACTED] laser treatments, [REDACTED] and will be followed at [REDACTED] 12 weeks post final treatment [REDACTED]). The number of treatments as well as the interval between treatments will be determined at the Investigator's discretion. In addition, subjects will complete a 3-day post treatment phone survey after each treatment. [REDACTED]

[REDACTED]

[REDACTED]

[REDACTED]

4.1 Study Endpoints

4.1.1 Exploratory Endpoints

4.1.1.1 *Safety Endpoints*

- Incidence and severity of adverse device effects at 2 weeks post-first treatment.
- Incidence and severity of adverse device effects during the study period, including subject pain level during laser treatment.

4.1.1.2 *Efficacy Endpoints*

- Degree of improvement in the treated area at 12 weeks post-final treatment as assessed by the Investigator (Physician's Global Assessment of Improvement).

[REDACTED]

4.2 Study Duration

Subjects enrolled in this trial will participate for approximately 5 to 16 months, [REDACTED]

[REDACTED]

[REDACTED]

[REDACTED]

[REDACTED]

[REDACTED]

[REDACTED]

The screening and first laser treatment may be combined into one visit provided that the informed consent process has been completed (see Section 12.2) and the subject has signed the IRB-approved Informed Consent Form **prior to** the commencement of any study-related procedures and device treatments.

4.3 Study Effectiveness Assessments

4.3.1 Investigator Assessments

4.3.1.1 *Investigator's Global Assessment of Improvement*

At 12 weeks post-final treatment, the Investigator will be asked to rate the degree of improvement in the appearance of the subject's treated area from baseline using the Physician's Global Assessment Scale:

4 = Very Significant or Complete Clearing ([REDACTED])

3 = Significant Clearing ([REDACTED])

2 = Moderate Clearing ([REDACTED])

1 = Mild Clearing ([REDACTED])

0 = No Clearing ([REDACTED])

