4.3.2 Subject Assessments

4.3.2.1 [REDACTED]

[REDACTED]

[REDACTED]

[REDACTED]

[REDACTED]

[REDACTED]

[REDACTED]

[REDACTED]

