4.5 Photographs

Standardized digital photographs will be taken of each subject's treatment area at baseline, prior to all laser treatments and at each follow-up. Any jewelry will be removed from the area being photographed. For facial photographs, hair will be pulled away from the face with a headband and subject will have recently cleansed skin. Photographs will be taken prior to all laser treatments and at each follow-up visit. Facial photographs will be obtained from 3 angles: with the subject facing forward, 90° to the right and 90° to the left. Photographs will be taken in the same windowless room equipped with adequate lighting. The room lighting, camera positioning and subject positioning should be consistent for all study visit photographs. Digital camera settings should remain the same for all photographs and the highest resolution settings should be utilized.

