7.2 Recording ADEs and SADEs

All ADEs/SADEs will be: (1) evaluated and must be recorded in the subject's medical chart and in the study case report forms (CRFs); (2) monitored and tracked from the time of the first treatment with the Cutera Enlighten laser system.

At each contact with the subject, the investigator must seek information on ADEs/SADEs by specific questioning and, as appropriate, by examination. ADEs/SADEs may be observed by the investigator and/or clinical research staff, elicited from the subject and/or family member or volunteered by the subject. All observed and volunteered adverse signs and symptoms, anticipated or unanticipated, regardless of severity or frequency, will be recorded in the case histories (medical chart and CRFs). Included in the description should be the nature of the sign or symptom, the date of onset, date of resolution (duration), the severity, anticipated or unanticipated, the relationship to study treatment or other therapy, the action taken (if any), and the outcome.

All SADEs, anticipated or unanticipated, must be reported to Cutera immediately but not later than 5 working days. The SADE must be recorded in: (1) the AE CRF and (2) a written report must be submitted to Cutera within five (5) working days after the investigator first learns of the event and is to include a full description of the event and sequelae, in the format detailed by the Cutera Serious Adverse Device Effect Form.

7.3 Follow-up of Subjects after ADEs and SADEs:

All reported ADEs/SADEs should be followed until resolution or until the subject's participation in the study ends. Resolutions of ADEs/SADEs are to be documented on the appropriate CRFs. All ADEs that result in permanent discontinuation from this clinical trial, whether serious or not, should also be reported on the subject Non-Completion of Study Form.

8 Potential Risks / Benefits

8.1

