10.3.1.1 Efficacy Analyses

Descriptive statistics such as mean, standard deviation, median and range will be performed for:

- The degree of improvement at 12 weeks post-final treatment as assessed by the Investigator, using the Physician's Global Assessment tool.
- [REDACTED]
[REDACTED]

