10.3.1.2 Safety Analyses

The safety variables for this study are:

- Incidence and severity of adverse effects during study duration (to be displayed descriptively as counts and frequency distributions)
- Subject discomfort (pain) during treatment (to be descriptively displayed).

Enrolled subjects who received at least one treatment will be included in the safety analyses. Device-related and procedure-related adverse effects (AEs) and subjects who prematurely terminate from the study due to an adverse device effect, including the treatment-related pain ratings, as reported on case report forms will be tabulated and analyzed. For a given AE term, counting will be done by subject, not by event, i.e. for a subject reporting the same AE more than once, the event will be counted only once, at the most severe and most-related occurrence. The number and percentage of subjects experiencing each AE Term will be descriptively summarized. Statistical hypothesis testing will not be performed for safety data.

Interim analyses of adverse events and adverse device effect incidence and severity will be performed when all treated subjects have completed the 12 week post-final treatment visit. At the conclusion of the study, complete analyses of the safety variables will be displayed descriptively.

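### The Investigator improvement scale has no grade for worsening, so a subject who looks worse than baseline is pooled with unchanged subjects (minor, optional change)

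*Combined protocol and SAP*

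**What the plan says.** Section 4 describes the trial in these words: "This is a single-center prospective, open-label, uncontrolled feasibility study". It enrols at most 20 subjects. The one legible efficacy endpoint in Section 4.1.1.2 is "Degree of improvement in the treated area at 12 weeks post-final treatment as assessed by the Investigator".

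Section 4.3.1.1 gives the instrument: "At 12 weeks post-final treatment, the Investigator will be asked to rate the degree of improvement in the appearance" of the treated area, with baseline as the reference. Five grades are listed. The highest, 4, stands for very significant or complete clearing, and the lowest, 0, stands for no clearing. The bracketed text beside each grade is redacted. No grade lies below 0.

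For the analysis of this score, Section 10.3.1.1 says: "Descriptive statistics such as mean, standard deviation, median and range will be performed for" the 12-week Investigator rating. Section 10.3 plans no formal statistical analysis, and Section 10.3.1 says that missing data will not be imputed.

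**The concern.** The rating compares the treated area with baseline, and appearance can move either way from baseline. The treatment targets in Section 4 include pigmentation, redness and skin texture. With 0 as the lowest grade, a subject who looks worse and a subject who looks the same get the same number. Once that number is recorded, no summary of it can tell them apart.

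There is no control group, so a reader will look to this score for the legible evidence on efficacy. The background section also says that the study is meant to inform the optimal range of treatment parameters. For that purpose, no effect and a worse appearance are different results, and the Investigator rating reports them as one.

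**Working it through.** The plan has no figure to reproduce: it gives a cap of 20 subjects and no sample-size calculation, significance level or power. The check is a bounds argument with worked examples.

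**Inputs from the documents.** Scores are 0, 1, 2, 3 or 4 (Section 4.3.1.1). The number of subjects is at most 20 (Section 10.1). The summaries are mean, SD, median and range (Section 10.3.1.1).

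**Assumed for illustration.** The numbers of better and worse subjects, and a signed net change in whole grades. The documents give neither. The recorded score is taken as max(0, net change).

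**Step 1, bounds.** If every score is at least 0, then the minimum, median and mean are at least 0. Twenty unchanged subjects give mean 0, SD 0, median 0 and range 0 to 0. Twenty subjects who are each one grade worse give exactly the same output, although their net mean is −1.

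**Step 2, size per subject.** Recorded mean − net mean = (sum of grades of worsening) / n. One subject one grade worse among 20 gives 1/20 = 0.05. With fewer rated subjects the shift per subject, 1/n, is larger.

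**Step 3, examples with n = 20.**

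| Better / worse / unchanged | Net mean | Recorded mean | Median, net and recorded |
|---|---|---|---|
| 4 at +1, 4 at −1, 12 at 0 | (4 − 4)/20 = 0.00 | 4/20 = +0.20 | 0 and 0 |
| 4 at +1, 6 at −1, 10 at 0 | (4 − 6)/20 = −0.10 | 4/20 = +0.20 | 0 and 0 |
| 4 at +1, 10 at −2, 6 at 0 | (4 − 20)/20 = −0.80 | 4/20 = +0.20 | −1 and 0 |

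All three rows give the same recorded data as 4 mildly improved and 16 unchanged subjects: mean 0.20, SD 0.41, median 0, range 0 to 1.

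**Step 4, counts per grade.** The phrase introducing the summaries is illustrative, so a frequency table is not excluded. On the 0–4 grades, however, each row above would show 16 subjects at 0 and 4 at 1. A frequency table helps only if there is a category for worse.

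**Step 5, with one added category.** Row 1 becomes 4 worse (20%), 12 unchanged (60%) and 4 at grade 1 (20%). Row 3 becomes 10 worse (50%), 6 unchanged (30%) and 4 at grade 1 (20%). With *worse* counted as 0, the planned mean stays at 0.20 in both, but the reader can now tell the two cohorts apart.

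**The case against.** **The score is labelled as improvement.** The endpoint, the instrument and the analysis all speak of degree of improvement, and every grade is a degree of clearing. Read that way, 0 is a correct score for a worsened subject. Naming baseline as the reference does not turn the scale into one of net change. This stands: the plan does not contradict itself, and the 0.05 and 0.20 figures apply only if the score is read as net change. Even under the improvement-only reading, the rating cannot say how many subjects look worse.

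**Worsening has another route.** Adverse device effects are assessed at each visit after the first treatment (Section 4.4.1). Section 7.2 says: "All observed and volunteered adverse signs and symptoms, anticipated or unanticipated, regardless of severity or frequency, will be recorded". Section 10.3.1.2 adds: "The number and percentage of subjects experiencing each AE Term will be descriptively summarized". This largely stands, and a reader who infers that the plan hides harm would go beyond the documents. The route is still not a full substitute. Severity there is graded by need for treatment and interference with daily activity, not by appearance against baseline. A gradual change that nobody regards as an adverse sign could be missed, and the documents give no basis for how often.

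**Redaction.** The section headed "4.3.2 Subject Assessments" is redacted, as are further efficacy items in Sections 4.1.1.2, 10.3 and 10.3.1.1. Another measure may record worsening, so it cannot be inferred that this score is the trial's only efficacy evidence. The redacted brackets beside the grades do not remove the point. If the one beside 0 covers both no change and worsening, the two are still pooled.

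**The effect is small.** In the first two examples the planned median is 0, and a mean of 0.20 beside it would hardly pass for a clear benefit. A reader might infer that the missing grade could produce an impressive result. It could not: counting worsened subjects as 0 cannot explain a mean of 2 or 3.

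**Conclusion.** The point holds as a minor one. The listed grades stop at 0, so the Investigator rating pools worsened with unchanged subjects, and neither the planned summaries nor counts of the 0–4 grades can show worsening. Relative to net change, the mean rises by 0.05 per grade for each worsened subject among 20. The +0.20 against 0.00 example rests on assumed counts, not on any rate in the documents.

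Severity is low. The study is exploratory with at most 20 subjects, and no test, sample-size calculation or stated success threshold depends on this score. Adverse signs are recorded separately, and unseen measures may fill the gap. The legible text does not support a claim that the efficacy result is invalid or that harm would go unreported.

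**What to change.** In Section 4.3.1.1, add a *worse than baseline* category to the Investigator scale. In Section 10.3.1.1, report the number and percentage of subjects in each grade, including *worse*. Keep the planned mean, SD, median and range on the 0–4 scale with *worse* counted as 0, so that those summaries keep their planned meaning.

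The cost is one more category on the form and one more table row, with no added visit or procedure. The limit is that a single category shows how many subjects worsened, not by how much. In the example with ten subjects two grades worse, it would report ten worse but not the net mean of −0.80. That is enough to tell no effect from a worse appearance, and a finer scale is hardly needed at this sample size.

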4.3.2 Subject Assessments

4.3.2.1 [REDACTED]

[REDACTED]

[REDACTED]

[REDACTED]

[REDACTED]

[REDACTED]

[REDACTED]

[REDACTED]

4.4 Study Safety Assessments

4.4.1 Incidence and Severity of Adverse Events:

Following the first laser treatment, adverse device effects (ADEs) will be assessed post-treatment and at each subsequent subject visit using the following scale:

1= mild: requires minimal or no treatment and does not interfere with the Subject's daily activities.
2= moderate: may cause some interference with functioning.
3= severe: interrupts Subject's usual daily activity and may require treatment.

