4.4.3 Phone Follow-up

Phone follow-up will be conducted for all subjects by the Investigator's staff at 3 days after each laser treatment. Data recorded on the phone follow-up questionnaire will be evaluated for adverse events, event duration and adverse event resolution. The Phone Follow-up Questionnaire is presented in **Appendix 5**.

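### A pigment change, scar or textural change still unresolved at the last visit can be graded mild, and the planned safety tables do not show whether it resolved, although resolution is recorded.

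*Combined protocol and SAP*

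**What the plan says.** Four parts of the combined protocol and SAP bear on this.

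- **Severity scale (Section 4.4.1).** Grade 1 is "1= mild: requires minimal or no treatment and does not interfere with the" subject's daily activities. Grade 2 is "2= moderate: may cause some interference with functioning". Grade 3 is "3= severe: interrupts Subject's usual daily activity and may require treatment".
- **What is recorded (Section 7.2).** Each event's description includes "the date of onset, date of resolution (duration), the severity, anticipated or unanticipated", together with its relationship to treatment, the action taken and the outcome. Events are followed until they resolve or the subject leaves the study.
- **Phone follow-up (Section 4.4.3).** Data from the call 3 days after each treatment are to be "evaluated for adverse events, event duration and adverse event resolution".
- **Safety analysis (Section 10.3.1.2).** The adverse-effect variable is "Incidence and severity of adverse effects during study duration (to be displayed descriptively as counts and frequency distributions"). Pain ratings and premature terminations due to an adverse device effect are also tabulated. Results are given by adverse-effect term. A subject who reports the same term more than once is counted once, at the worst grade and closest relationship. The interim look in the same section likewise covers incidence and severity.

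**The concern.** The severity scale measures how far an effect disturbs the subject's day and whether it needs treatment. For a device used to improve appearance, a mark that limits nothing and needs no treatment but does not go away is also a relevant harm. The scale cannot express that, and the planned tables do not supply it by another route.

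The protocol itself treats this kind of harm as relevant. Its background says that "hypo- or hyperpigmentation, prolonged wound healing and even scarring can occur following ablative procedures". That sentence concerns ablative lasers, not this device. However, Section 5.1.2 excludes people with a tendency to pigment change (criterion 16) or a history of keloid, hypertrophic scarring or abnormal healing (criterion 9), and Section 5.1.1 admits all Fitzpatrick types, I to VI.

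Safety is a stated objective, and Section 10.3 plans no formal statistical analyses, so the descriptive tables are the safety result. If they cannot separate an effect that cleared from one that did not, a summary that effects were mild could be accurate under the plan and still leave persistence unreported.

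**Working it through.** The plan gives no figure to reproduce. Enrolment is a ceiling of 20, with no rate, precision or hypothesis attached. The check is to read the sections against each other and then follow an example through the planned table.

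**Step 1: can an unresolved lesion be graded 1?** Grade 1 has two conditions: minimal or no treatment, and no interference with daily activities. No grade refers to duration, reversibility or visible sequelae. A lesion that meets both conditions is grade 1 whether it lasts 3 days or is still present at the last visit. A lesion that interferes with functioning would not be. So the result is *can be graded mild*, not *will be*.

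**Step 2: does the analysis recover persistence?**

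| Item | Recorded (7.2) | Output in 10.3.1.2 |
|---|---|---|
| Nature of event | yes | yes, by term |
| Severity | yes | yes |
| Relationship | yes | yes, through the counting rule |
| Onset and resolution dates | yes | none |
| Outcome | yes | none |

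Pain ratings and terminations due to an adverse device effect are additional outputs, but neither shows whether an effect resolved. The phone call evaluates duration and resolution only 3 days after a treatment. Participation runs to about 5 to 16 months (Section 4.2), so the call is too early to show persistence, and Section 10 names no output from it.

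**Step 3: what does the counting rule do with repeat events?** Suppose a subject has the same term twice: once at grade 2, resolved, and later at grade 1, unresolved. With equal relatedness, the rule keeps the grade 2 occurrence. The unresolved one leaves the table. Attaching a duration to the retained record would therefore not be enough.

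**Step 4: illustration.** The counts are assumptions: 20 treated subjects, three of them with the same pigment-change term, all grade 1.

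- Planned entry: 3/20 = 15%, mild, whether the three cases resolved or not.
- If all three resolved, an unresolved count would read 0/20 = 0% (exact 95% interval 0% to 16.8%).
- If none resolved, it would read 3/20 = 15% (exact 95% interval 3.2% to 37.9%).

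The intervals are Clopper-Pearson. They show only how imprecise such counts are at this size.

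**Step 5: limit of the added output.** The chance that at least one of 20 subjects has an unresolved effect is 1 − (1 − p)^20. For assumed true rates p of 2%, 5% and 10% this is 33%, 64% and 88%. An empty unresolved column would therefore be weak reassurance, but it would at least be reported.

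**The case against.** The strongest reply is that this is a small, uncontrolled exploratory study, that duration and outcome are on the case report forms, and that they can be listed at reporting. No data are lost. That is true, and it makes this a reporting gap, not a flaw in conduct. It does not remove the gap, because the scale and counting rule, followed exactly, produce a result that cannot show persistence.

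Several stronger readings are tempting, and the documents do not support them.

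- *A brief redness and a lasting pale patch would share one cell.* Section 10.3.1.2 tabulates by term, so effects recorded under different terms have separate rows and a reader would see that pigment change or scarring occurred. Transient and unresolved effects merge within a term.
- *Such lesions will be reported as mild.* Interference with functioning would move a lesion out of grade 1, and the documents do not say how often that would happen.
- *Permanent damage is hidden.* Permanence cannot be established within participation of about 5 to 16 months. Unresolved at last contact is the most the data can say.
- *Only incidence and severity are analysed.* Pain, terminations due to an adverse device effect and relatedness are also covered.
- *Nothing else would catch a lasting lesion.* The definition of a serious adverse device effect in 7.1 is not visible, and the risk list in 8.1 is not readable. Some lasting lesions might be classed as serious whatever their grade. That would still give no resolution summary for the rest.

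A reader might also want a rule that a mild grade cannot support acceptable safety when the effect is unresolved. The study states no acceptance criterion, so such a rule would introduce a decision standard the plan does not have.

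**Conclusion.** The point holds in a limited form. An effect that is unresolved at the last visit can be graded mild, and within one adverse-effect term it gives the same table entry as one that cleared, although the plan records what is needed to tell them apart. In the illustration, an entry of 15% mild is compatible with anything from none to all of the three cases being unresolved.

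This rests on the visible text of Sections 4.4.1, 7.2 and 10.3.1.2, and on the assumption that the withheld definitions in 7.1 do not route every such lesion to separate reporting. The counts and rates used are assumptions, not predictions. The change should be made before the safety tables are produced. It affects what the study can say about safety, not the validity of the data collected.

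**What to change.** Leave the severity scale unchanged. Add three outputs to Section 10.3.1.2, all from fields that Section 7.2 already requires:

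1. For each adverse-effect term, the number and percentage of subjects with any occurrence unresolved at the visit 12 weeks after the final treatment, and at last contact. Count a subject if any occurrence is unresolved, even if another was more severe. Because the analysis-set section (10.3.1) imputes nothing, show subjects not seen at the 12-week visit as a separate count.
2. The duration of each event, with unresolved events shown as ongoing and censored at last contact. A plain median from onset and resolution dates would drop exactly these events, since they have no resolution date, and would make durations look shorter than they were.
3. A by-subject listing of every pigment, scar or textural event, with grade, onset, duration and outcome.

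The cost is one extra table and one listing for at most 20 subjects. No new data, visits or procedures are needed.
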